Inclusion criteria: Individuals who have an abnormal screen that is due for follow-up including:

- Breast: women 40-80 years with an *incident* (i.e., newly detected) abnormal screening mammogram or digital breast tomosynthesis (DBT) exam.
- Cervical: women 21-65 years with an *incident* abnormal screening Pap.

- Colorectal: adults 40-80 years with an abnormal screen, including *incident* FOBT/ FIT, or *prevalent* colonoscopy. Because of the long periods of time required for follow-up of colonoscopies, we will look back over a 5-year period and will therefore find *prevalent* abnormalities that become due for follow-up.
- Lung: adults 55-80 years, current and former smokers, with an *incident* abnormal LDCT result.

Definition of the specific screening abnormalities and timing of diagnostic evaluation are based on our prior work, expert opinion, and the literature. Need for follow-up will be determined by the lack of an appropriate clinical test within the specified time as documented in the EHR.

Exclusion criteria: We will exclude patients who: 1) are not English or Spanish-speaking, or 2) have had prior cancer of the organ for each screening test (i.e., women with prior breast cancer will not be tracked for breast cancer screening abnormalities) as these individuals may have non-standard follow-up care recommendations.

Intervention Design and Randomization Scheme. We will perform a 4-arm cluster RCT with randomization done at the practice-level, across the participating practices. We have chosen this level of randomization as it would be logistically complicated for the practices to have different patients randomized to different intervention components (i.e., reduced contamination). While we have received the approval of the primary care network leadership of the participating networks and have discussed the study with practice leadership, practices will be given the opportunity to opt-out of the study before practices are randomized. Randomization will be stratified based on: (1) practice size, (2) percent female, and (3) percent of patients on Medicaid as a marker for socioeconomic status.

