(1) Practice and Provider Engagement. We have obtained support of network leadership for the study. Investigators have/ will attend practice meetings at intervention sites to integrate work flow with practice routines and educate staff about the study and its procedures. PCPs will not be required to do recruitment; identification of eligible patients will be done centrally using the IT platform described above. We therefore anticipate a high level of practice and PCP participation since the intervention does not constrain usual practice, but adds additional systems beyond those currently available. As noted above, practices and providers will be given the opportunity to opt-out of the study before practices are randomized.

(2) Patient Identification and Enrollment. The mFOCUS platform will incorporate algorithms to identify eligible patients and patient-practice attribution. All patients will remain under the direction of their personal PCP/ practice and the intervention components will facilitate the delivery of care in addition to the current standard of care.

We plan to enroll 3324 eligible participants (approximately 831/ arm – as randomization will be done at the practice level the arms will not be the same size) across the 3 participating primary care networks (BWH, MGH, and Dartmouth). We anticipate that recruitment will be somewhat higher at BWH and MGH than Dartmouth as the networks are bigger. Because randomization will be done at the practice level, we will not be able to recruit exactly 3324 individuals (patients will be in process of recruitment since they will be recruited in batches) – this is the number suggested by our sample size calculation. We anticipate that this calculations will need to be updated due to the impact of COVID-19 and that our recruitment number will be higher because of the back log of testing that will occur as hospitals reopen for screening procedures. We anticipate that we could possibly enroll up to 9,000 eligible patients at MGH/BWH, and 12,000 eligible patients study wide. We will not exceed recruitment of 12,000 eligible individuals. Due to the way our IT system is configured, we anticipate that we could review up to 20,000 patient charts study wide. Not all of the patient charts reviewed will be deemed eligible.

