Secondary analyses will model time-to-follow-up, using a clustered proportional hazards regression to examine whether abnormal screens are followed-up as quickly as possible. Patient-level time-to-follow-up will be recorded with censoring at the end of study for patients who never received follow-up. Patients will be clustered within providers using the generalized estimating equation approach, implemented as a “frailty” analysis in the SAS Phreg procedure. An additional correlation component for patients within practices cannot be included, but we will evaluate the robustness of our findings by using an alternative model, clustering by practice rather than provider. Predictors and covariates in this model will be identified in the same way as described above. The proportional hazards assumption for the intervention effects will be verified by entering a time-varying version of those predictors. Other secondary outcomes based on patient, provider and team surveys will use clustered linear regression models to compare satisfaction scores between study arms. Our secondary system outcome: the number of patient contacts; will be compared between arms using clustered Poisson regression. The model building will be analogous to the approach detailed above.

We will also consider several exploratory analyses. In particular, we will perform our primary and secondary analyses within each of the four types of cancer and by risk of cancer. Prior to any of these subgroup analyses, we will put the appropriate interaction terms into the primary models above. However, it was not practical to design this study to have sufficient power to pursue all of these possibilities. Instead, any “findings” in these secondary analyses will be considered as clues to be pursued in future studies and in alternative databases.

Finally, while it would be clinically important to pursue cancer detection rates, we will not do so here because we lack statistical power and because of the possibility that more cancers may be diagnosed in the intervention arms than the control arm because of higher follow-up rates with more diagnostic evaluations. We will not have long enough follow-up times to look at differences in cancer incidence related to inadequate follow-up. Instead we will perform descriptive analyses within each study arm to look at the number of incident cancers identified.

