Our sample size calculation was based on an increase in the follow-up test completion rate of 11-14% with the intervention- this would give us 80% power to detect an 11% difference in the follow-up rate. We have an adequate number of potential participants across our sites to achieve this sample size.

Specific Aim 2: To evaluate facilitators and barriers to the *Reach, Adoption, Implementation and Maintenance* of mFOCUS.

The RE-AIM framework (Reach, Effectiveness, Adoption, Implementation and Maintenance with Effectiveness assessed in **Aim 2**) will allow us to assess the multilevel implementation of our intervention. The primary goal is to inform and facilitate dissemination of the program in the 3 networks rather than to test specific hypotheses. We will calculate summary statistics and conduct bivariate comparisons across sites using Fisher's exact test, t-tests, and the Wilcoxon rank sum test where applicable for survey outcomes.

RE-AIM Metric	Measure	Data Source
Reach	• % of eligible individuals in each intervention group who engage in relevant step (open email reminder, speak with outreach coordinator or PN)	• Population management system
	• Patient barriers and facilitators of follow-up	• Patient survey
Adoption	• Barriers and facilitators to follow-up • Systems & processes for follow-up • Knowledge of and satisfaction with components of mFOCUS	• PCP survey
Implementation	• Technical and organizational barriers to implementation • Fidelity of delivery of the intervention	• PCP survey • Population management system
Maintenance	• Technical and organizational barriers to maintenance	• PCP surveys

Patient, and provider surveys are attached. Once the final version of the patient survey is approved it will be translated by an IRB approved vendor and submitted to the IRB.

Briefly describe study procedures. Include any local site restrictions, for example, "Subjects enrolled at Partners will not participate in the pharmacokinetic portion of the study." Describe study endpoints.

See study procedures described above. No local site restrictions are planned.

For studies involving treatment or diagnosis, provide information about standard of care at Partners (e.g., BWH, MGH) and indicate how the study procedures differ from standard care. Provide information on available alternative treatments, procedures, or methods of diagnosis.

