Trial: We plan to recruit 3324 participants in the RCT who fit the eligibility criteria defined above (are overdue for follow-up of an abnormal cancer screening test result). Because the trial is testing a “care enhancement” we are requesting a waiver of informed consent given the large number of subjects distributed over a maximum of 44 primary care practices. Randomization will be done at the practice level and individual patients will not be approached for recruitment. Because randomization will be done at the practice level, we will not be able to recruit exactly 3324 individuals (patients may be in process of recruitment since they will be recruited in batches) – this is the number suggested by our sample size calculation. We will not exceed recruitment of 12,000 eligible individuals. The outcomes for the main trial will be assessed using data from the electronic health records at BWH, Faulkner, MGH, NWH, NSMC, and DFCI. NWH, NSHM, and DFCI are included because patients from MGH and BWH may have tests that are performed at these sites, thus they will be included in our review for diagnostic testing. Because of the large number of study participants and the minimal risk, we request a waiver of informed consent for this portion of the trial. It would not be feasible to contact this number of individuals and as this is a pragmatic trial it would adversely affect the validity and interpretation of our results.

Surveys: Some of the outcomes of the study will be measured by PCP and patient surveys:

PCP Surveys-PCPs, excluding trainees, at participating sites using the electronic health record will be surveyed prior to launch of the RCT and 3 months after recruitment ends. Prior to fielding the survey, we will request that the primary care network director send an email to PCPs in his/ her network informing them about the purpose to the survey-will then receive an email from one of the study investigators with a link to a Redcap survey. Each PCP will receive up to 5 email contacts over 4 weeks. Remuneration is described in the appropriate section below.

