Since, some of the subgroup sample sizes will be limited, not all the covariates from the primary overall model above in (3) will be added to each stratified models. Decisions will be made based on the degree of confounding and the sample size.
- c. Appendix: A similar figure will be created for the mITT data. A decision of whether to display it in the appendix will be made based on the findings.

5. Exhibit 5: Figure 3: Kaplan-Meier Curves

- a. Four curves (4 arms), unadjusted, ITT
- b. Log-rank p-value
- c. A Cox regression model will be built for the ITT data. Since only one level of clustering is available, the model will use the analogue of random effects for practices and adjust for the same variables as in the logistic regression model above.
 - i. Significance testing will use a global p-value across all 4 arms and, if significant at $p<0.05$, pairwise comparisons between each arm and the control arm will be carried out. Results for the pairwise comparisons will be presented as 95% confidence intervals.
 - ii. The results of the Cox regression will be reported in the text. A table of the model results may appear in the Appendix.

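### The protocol's main time-to-follow-up model clusters by provider although practices are randomised; the SAP clusters the same outcome by practice, and neither text says which governs

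*Combined protocol and SAP*

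**What the plan says.** The protocol's design section states: "We will perform a 4-arm cluster RCT with randomization done at the practice-level". The recruitment section gives "a maximum of 44 primary care practices".

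Three pieces of text bear on time to follow-up and the other secondary outcomes:

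- **Protocol, Analysis Plan/Sample Size, secondary analyses** (protocol version dated January 6, 2023). For time to follow-up, "Patients will be clustered within providers using the generalized estimating equation approach", fitted as a frailty analysis. The protocol adds that a further practice component cannot be included, and that robustness will be examined with an alternative model clustered by practice.
- **SAP, Exhibit 5, item c** (SAP dated 5.19.2022). For the Cox model of the same outcome: "Since only one level of clustering is available, the model will use the analogue of random effects for practices".
- **Protocol, same paragraph, survey outcomes.** These "will use clustered linear regression models to compare satisfaction scores between study arms". The number of patient contacts gets a clustered Poisson model. No level is named for either, and model building is said to be analogous to what precedes. The SAP comments defer the survey outcomes to a second publication, so the SAP does not settle their level.

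The primary outcome is handled differently. Both the protocol and the SAP (Exhibit 3) put random effects for practice and physician in the logistic model.

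**The concern.** All providers in a practice share one arm. A model that clusters only by provider treats the providers of one practice as independent replicates of the intervention. Any variation between practices, such as scheduling capacity, local referral routes or patient mix, then enters the arm contrast but not its standard error. Confidence intervals are too narrow, and a chance difference between practices can be reported as an intervention effect on speed of follow-up.

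A practice-clustered model kept as a robustness check does not repair the headline p-value, and the protocol gives no rule for the case where the two models disagree. With the SAP naming the other model as the main one, the choice of reported result for a named secondary outcome is left open.

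**Working it through.** **1. The plan's own figure.** The documents give no ICC, so there is no stated clustering effect to reproduce. The nearest figure is the sample size: "We plan to enroll 3324 eligible participants (approximately 831/ arm", with "80% power to detect an 11% difference in the follow-up rate". Taking 50% against 61% (the protocol's background gives an average follow-up of about 50%; the design control rate is not stated), two-sided alpha 0.05/3 and no clustering, the usual two-proportion formula gives 427 per arm. The planned 831 then implies a design effect of 831/427 = 1.95. With 3324/44 = 75.5 patients per practice, the ICC is (1.95 - 1)/74.5 = about 0.0127. This is a back-calculation, not a stated input. It places the range used below, 0.01 to 0.03, around and above what the plan's size would imply.

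**2. Inputs.** m = 75.5 patients per practice (3324 participants, at most 44 practices, equal sizes assumed). g = 5 or 8 providers per practice, assumed, so q = m/g = 15.1 or 9.4 patients per provider. Practice ICC r = 0.01 or 0.03, assumed. Extra within-provider correlation is first set to zero.

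**3. Formulae.** Ratio of the true variance of the arm contrast to the variance reported under provider-only clustering:

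R = [1 + (m - 1)r] / [1 + (q - 1)r]

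True level of a nominal 5% pairwise test = 2 × [1 - Φ(1.96/√R)].

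| r | g | numerator | denominator | R | true level |
|---|---|---|---|---|---|
| 0.01 | 5 | 1.745 | 1.141 | 1.53 | 11.3% |
| 0.01 | 8 | 1.745 | 1.084 | 1.61 | 12.2% |
| 0.03 | 5 | 3.236 | 1.423 | 2.27 | 19.4% |
| 0.03 | 8 | 3.236 | 1.253 | 2.58 | 22.3% |

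**4. Extra within-provider correlation d.** The denominator becomes D = 1 + (q - 1)(r + d), and R = [D + (m - q)r]/D. With d = 0.02 and g = 5, R falls from 1.53 to 1.42 at r = 0.01 (level 10.1%) and from 2.27 to 2.06 at r = 0.03 (level 17.2%). The inflation shrinks but stays.

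**5. Wider range.** With r from 0.005 to 0.05, d from 0 to 0.02 and 4 to 12 providers per practice, the pairwise level is 7-31% at 3324 participants. Enrolment may go higher ("We will not exceed recruitment of 12,000 eligible individuals"). At 12,000, or 273 per practice, the level is 10-46%. The direction does not reverse anywhere in this range.

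**6. Check by simulation.** A four-arm Cox model was simulated under the null: 400 replicates, equal cluster sizes, provider log-hazard variance 0.03, practice variance 0.01-0.10, and cluster-robust variance. Clustering by provider rejected 9-39% of the time pairwise and 12-64% on the global test. Clustering by practice rejected 4-8% pairwise and 8-12% globally. Monte Carlo error is about 1 to 2.5 points. The remaining excess under practice clustering fits the use of an uncorrected robust variance with only 44 clusters.

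**7. Patient survey, if it were clustered by provider.** A 15% sample of 3324 is about 499 patients, or 11.3 per practice and about 2 per provider. At r = 0.01, R = 1.103/1.01 = 1.09 and the level is 6.1%. At r = 0.03, R = 1.309/1.03 = 1.27 and the level is 8.2%. Both are before non-response, which would lower them.

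**The case against.** The strongest reply is that the valid analysis is already planned. The SAP governs the primary results paper, lists time to completion as a secondary outcome and clusters it by practice. The protocol also commits to a practice-clustered model. The protocol is an IRB summary form, and its latest content includes administrative matter written after the study ended, so its later date does not show that the provider model was preferred to the SAP's. This stands in part. It reduces the problem to which model is the main one, and a reader should not infer from the dates that the protocol overrides the SAP. It does not remove the conflict, because neither text states precedence and only one of the two models respects the unit of randomisation.

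The protocol's remark that a practice component cannot be added is fairly read as a limit on fitting two levels at once, and the SAP says the same. That is a reason for choosing one level. It does not favour the provider over the randomised unit, and a robust variance aggregated by practice also covers correlation within provider.

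A reader might infer that the survey models cluster by provider too, with p-values far too small. The documents do not support that. No level is named, and the reference to the preceding approach could equally mean the primary model with both practice and physician. What can be said is that the level is unspecified.

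It is also fair that the ICC and the number of providers per practice are assumptions. They affect the size of the inflation, not its direction.

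**Conclusion.** The protocol's main time-to-follow-up model is wrong as written for a practice-randomised trial, and it contradicts the SAP. If it is followed, a nominal 5% pairwise test runs at roughly 11-12% (ICC 0.01) to 19-22% (ICC 0.03), assuming 44 equal practices, 5 to 8 providers in each and no extra provider correlation. If the SAP model is used, this inflation does not arise, apart from the small-sample issue with at most 44 practices.

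For the survey and contact-count models the finding is missing detail, not a demonstrated error. A reader might also extend the point to the primary 120-day outcome. That would be mistaken, since its model includes practice in both documents. The matter is confined to secondary outcomes and should be corrected.

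**What to change.** Amend the secondary-analysis paragraph of the protocol to agree with SAP Exhibit 5, item c:

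- Make practice the clustering level of the main time-to-follow-up model, by a practice-level frailty or a robust variance aggregated by practice.
- Add a small-sample correction suited to at most 44 practices, for example a bias-corrected robust variance or reference distributions with between-practice degrees of freedom. Add the same sentence to the SAP.
- Make the provider-clustered model a sensitivity analysis, and state that the practice-clustered result is the one reported.
- Name practice as the clustering level for the patient-survey, PCP-survey and contact-count models.
- State which document governs where the two differ.

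The cost is a few lines of wording and wider confidence intervals for time to follow-up than the provider model would give. No new data are needed.
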